14.7.1 Safety Early Stopping Rule

Early stopping of this trial is calculated based upon the report of study treatment (i.e., the combination of atezolizumab and tiragolumab, or atezolizumab monotherapy) related grade 3 or greater adverse events (AEs) (i.e., toxicities). A Bayesian safety-monitoring plan (Thall PF, Simon RM, Estey EH., 1996)²¹ will be implemented once the first 12 evaluable patients are available. A Bayesian sequential safety monitoring will be defined as $\Pr(\theta_T > \theta_0 \mid \text{data}) > 0.80$, where θ_T denotes the proportion of toxicity and θ_0 ($\theta_0=20\%$) represents the rate under null hypothesis (maximum probability of toxicity allowed). Enrollment will be stopped early whenever there is >80% chance that the event rate is larger than the null. The trial will be recommended to stop for excessive toxicities according to the toxicity stopping boundaries listed in the table below:

| Stop for excessive toxicities (grade 3 or greater) if: | |
|--|---|
| # patients who experience toxicity is \geq : | In first # patients being determined ctDNA positive |
| 4 | 12 |
| 7 | 24 |
| 10 | 36 |
| 12 | 48 |
| 15 | 61 |

The above stopping boundaries were obtained using Bayesian Toxicity Monitoring online application version 2.2.1.0 (available at <http://ibl.mdanderson.org/BTM/>) developed by M.D. Anderson Cancer Center. We assume that the parameter θ_0 is a constant and that θ_T follows a non-

informative prior of beta (0.5, 0.5). Accrual will be stopped and the event will be reviewed by the Data Safety and Monitoring Board if a study treatment-related death is observed.

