Treatment can continue for up to 13 cycles. For patients receiving both drugs, atezolizumab will be given first, followed by tiragolumab. If either study drug is delayed for a related toxicity, it is recommended that the other study drug is also delayed (if

applicable) since the safety profiles for atezolizumab and tiragolumab are similar.

All patients will receive CT scans every 12 weeks for the first two years after initiation of treatment, then every 24 weeks for the next year; frequency of scans will not be adjusted in the event of a treatment delay.

Administration of First and Subsequent Infusions of Atezolizumab and Tiragolumab

| Study drug | First Infusion | Subsequent Infusions |
|---|---|---|
| Atezolizumab infusion | 
 • No premedication is permitted prior to the atezolizumab infusion. • Vital signs (pulse rate, respiratory rate, blood pressure, and temperature) should be recorded within 60 minutes prior to the infusion. • Atezolizumab should be infused over 60 (\pm 15) minutes. • If clinically indicated, vital signs should be recorded every 15 (\pm 5) minutes during the infusion. | 
 • If the patient experienced an IRR with any previous infusion of atezolizumab, premedication with an antihistamine and/or antipyretic medication may be administered for subsequent doses at the discretion of the investigator. • Vital signs should be recorded within 60 minutes prior to the infusion. • Atezolizumab should be infused over 30 (\pm 10) minutes if the previous infusion was tolerated without an IRR or 60 (\pm 15) minutes if the patient experienced an IRR with the previous infusion. • If the patient experienced an IRR with the previous infusion, or if clinically indicated, vital signs should be recorded during the infusion. |

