5.3 Definitions of Evaluability

In order to be evaluable for the primary objective (ctDNA negativity at C3D1), a patient must have blood drawn to assess ctDNA at that time point. Patients in Stage 1 who discontinue treatment prior to C3D1 will be replaced; patients in Stage 2 who discontinue treatment prior to C3D1 will not be replaced.

All patients who receive any study treatment are evaluable for toxicity. Patients are evaluated from first receiving study treatment until a 90-day follow up after the conclusion of treatment or death.

All patients are evaluable for disease response unless they discontinue participation prior to having any disease assessment.

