14.3 Secondary Endpoints

- Confirmed ctDNA negative rate, defined as the proportion of ctDNA-positive patients having two consecutive negative ctDNA tests.
- Relapse free survival (RFS), defined as the duration of time from the date of positive ctDNA being confirmed to the date of earliest disease relapse or death, whichever occurs first. Patients who neither relapse nor die by the data cutoff date will be censored at the last follow up date.
- Distant metastasis free survival (DMFS), defined as the duration of time from the date of positive ctDNA being confirmed to the date of appearance of a distant metastasis or death, whichever occurs first. Patients who neither develop distant metastasis nor die by the data cutoff date will be censored at the last follow up date.
- Overall survival (OS), defined as the duration of time from the date of positive ctDNA being confirmed to death from any cause. Patients who are alive by the data cutoff date will be censored at the last follow up date.

- Safety and tolerability will be defined as the number of treatment (i.e., atezolizumab and tiragolumab) related grade 3 or greater adverse events (AEs). Adverse events will be assessed using CTCAE v5.0 criteria. Safety will be monitored from the time of initiation of study treatment to 30 days after discontinuation of therapy.

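### The toxicity rule should act as soon as a row's count is reached, even before patient 12, and should say that each row stays open while its patients are still being observed

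*Combined protocol and SAP*

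**What the plan says.** Section 14.7.1 stops accrual for excess study-treatment-related Grade 3 or higher events. The criterion is a posterior probability above 0.80 that the toxicity rate exceeds 20%, under a Beta(0.5, 0.5) prior. The table gives five rows: 4 in 12, 7 in 24, 10 in 36, 12 in 48 and 15 in 61. The monitoring plan "will be implemented once the first 12 evaluable patients are available". The same section adds: "Enrollment will be stopped early whenever there is >80% chance that the event rate is larger than the null". Separately, any study-treatment-related death stops accrual and goes to the DSMB, with no patient threshold.

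Section 5.3 sets who counts: "All patients who receive any study treatment are evaluable for toxicity". It gives no minimum number of cycles or days. Section 5.2 says: "Treatment can continue for up to 13 cycles".

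Two related items do not agree. The text of 14.7.1 counts evaluable patients, while the table's column counts patients found ctDNA-positive. On the window, Section 5.3 says "Patients are evaluated from first receiving study treatment until a 90-day follow up after the conclusion of treatment or death" and Section 7.0 also uses 90 days, but Section 14.3 says "Safety will be monitored from the time of initiation of study treatment to 30 days after discontinuation of therapy".

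**The concern.** The point is when a row is read, not what its count is.

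**Before patient n.** Once four of the first few patients have had a qualifying toxicity, later patients cannot undo it, and the 4-in-12 row is certain to be met. A rule not in force until 12 still lets enrolment run on to 12.

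**At patient n.** The beta-binomial calculation behind the table treats each of the n patients as having a final yes/no result. A patient dosed yesterday counts as evaluable and, with no event so far, enters as a non-event. If a row were read at that moment and never again, the 80% criterion would be applied to an undercount. The text sets no minimum observation and does not say outright that a passed row is reopened when one of its patients later has an event.

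At stake is how many patients are enrolled on a regimen that is too toxic by the plan's own standard before accrual stops.

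**Working it through.** **1. Reproduce the table.** With x toxicities in n patients the posterior is Beta(0.5 + x, 0.5 + n − x). The boundary is the smallest x with P(rate > 0.20) > 0.80.

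| Row | Posterior at the row | With one fewer event |
|---|---|---|
| 4 in 12 | 0.874 | 0.688 |
| 7 in 24 | 0.868 | 0.740 |
| 10 in 36 | 0.876 | 0.779 |
| 12 in 48 | 0.809 | 0.703 |
| 15 in 61 | 0.817 | 0.725 |

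All five counts are correct for complete data.

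**2. Waiting for patient 12.** Four events in the first 5 patients give Beta(4.5, 1.5) and a posterior of 0.998, and guarantee at least 4 of 12. With prompt onset (assumption), the chance that the fourth event has occurred by patient 11 is P(Bin(11, p) ≥ 4). At p = 0.40 this is 1 − (0.0036 + 0.0266 + 0.0887 + 0.1774) = 0.704. At 0.30 and 0.50 it is 0.430 and 0.887.

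The mean number of patients saved by acting at once is the sum over t = 4 to 12 of (12 − t)·C(t − 1, 3)·p⁴(1 − p)^(t − 4). Over all trials this is 1.5, 2.8 and 4.2 at 30%, 40% and 50%. The chance of meeting the first row is unchanged by acting early: 50.7%, 77.5% and 92.7%, and 20.5% at a true rate of 20%.

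**3. Immature patients.** Inputs: 61 treated patients (Section 14.5), 24 months of accrual (Protocol Summary) and 13 cycles of 28 days. Even accrual gives 24/61 = 0.393 months between patients. When patient 12 is first dosed, mean follow-up of the twelve is 5.5 × 0.393 = 2.2 months. The full window is 13 × 28 = 364 days plus 30 or 90 days, about 13 or 15 months.

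Dilution: 3 events in 8 fully observed patients give 0.888, above 0.80. Adding 4 just-dosed patients as non-events gives 3 of 12, or 0.688.

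**4. Does it matter whether rows stay open?** Simulation: 6,000 trials per scenario, random arrivals at 61/24 = 2.54 per month, an assumed true rate of 40% over 15 months. Onset is truncated exponential with median parameter 2 or 4 months, or uniform.

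| Mean enrolled when accrual ends | 2 months | 4 months | Uniform |
|---|---|---|---|
| Each row read once, when patient n starts | 32 | 41 | 53 |
| Row applies from patient n, then stays open | 21.1 | 26.0 | 34.6 |
| Row applies from the first patient and stays open | 20.5 | 25.8 | 34.6 |

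Under read-once, the first row is crossed in 17%, 5% and under 1% of trials, against 77.5% with complete data. Nearly all the loss comes from reading once; the start at 12 adds little when onset is delayed.

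**5. False stopping.** At a true rate of exactly 20%, exact recursion over the five rows gives 20.5 + 7.3 + 3.8 + 6.1 + 3.2 = 40.9% with complete data.

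**The case against.** A reader might infer that the rule counts barely observed patients as toxicity-free for good, so that a too-toxic regimen passes the early rows and 11 to 18 extra patients are enrolled (32 − 21, 53 − 35). The documents do not support that. The figure needs each row to be read once and closed, and no passage says so. Section 14.7.1 calls the monitoring sequential and stops enrolment whenever the criterion is met. Its rows refer to a fixed first set of patients, whose count can rise later. Section 12 requires the periodic safety reports to carry the early stopping rules with supporting data. A six-monthly re-read alone (timing assumed) brings the means to about 26, 32 and 41. At the slower minimum enrolment pace in Section 4.6, even read-once gives about 28, 34 and 45.

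Other safeguards also count. A treatment-related death stops accrual at any time, and Section 12 has the principal investigator and coordinator watch for serious toxicities continuously. The wait to 12 therefore concerns non-fatal events only. A minimum before formal looks is also defensible: under this prior, 1 event in 2 patients already exceeds 0.80, and adding a look at 6 patients would raise false stopping at 20% from 40.9% to 52.6%.

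Finally, the two halves bite under opposite conditions, prompt and delayed onset, so their effects should not be added.

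What stands: investigator review has no numerical boundary. The DSMB meets six-monthly, starting six months after the first secondary-site enrolment, and about 15 patients (6 × 2.54) enter in six months. No sentence says that rows stay open. None of the defences justifies enrolling to 12 once the fourth event has occurred.

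**Conclusion.** The concern holds as two wording gaps, not as a failed rule. The table is right.

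The start at 12 literally delays action after a fourth non-fatal event that already settles the first row. With prompt onset that situation arises in 43% to 89% of trials at true rates of 30% to 50%, at a mean cost of about 1.5 to 4 patients.

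On re-reading, the text is ambiguous and leans towards open rows. Under that reading there is almost no loss; under read-once, mean enrolment at a 40% rate would be about 32 to 53 instead of about 20 to 35.

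The toxicity rates and onset patterns are assumptions, since the documents give neither for this population. The accrual pace assumes that 61 patients enter over 24 months.

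**What to change.** Keep every count in the table and add to Section 14.7.1:

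- **Live rows.** Each row applies from the first patient. Accrual stops and the DSMB is convened as soon as the row's count is reached among the first n patients, even before patient n is enrolled. This is a free improvement: a row met early is certain to be met at n, so no false stops are added and no new boundary is created.
- **Open rows.** Each row stays open until its n patients complete the toxicity window, with a recheck at every new related Grade 3 or higher event. This is a cheap improvement. It gives the table's own complete-data stopping chance of about 41% at a true rate of 20%. Immature single looks would show a lower figure only because they undercount.
- **Reconcile.** Use one denominator, since evaluable and ctDNA-positive patients are different sets and a patient never dosed cannot have a related event. Use one toxicity window across Sections 5.3, 7.0 and 14.3.

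The cost is a few sentences and a short recheck by the statistician per event.

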14.5 Sample Size Determination

Under Simon's two-stage optimal design (Simon, 1989), with one-sided alpha = 0.05 and power = 0.8, assuming using atezolizumab and tiragolumab will have a ctDNA clearance rate of 25% and a null rate is 10%, in stage 1, 18 patients will be accrued for the treatment arm (atezolizumab + tiragolumab). If 3 or more patients are observed to be ctDNA-negative at C3D1 for the treatment arm, we will continue the treatment of atezolizumab and tiragolumab to stage 2 with an additional 25 patients being accrued. Otherwise the study will be stopped. If 8 or more ctDNA clearances are observed at the study completion, the combination of atezolizumab and tiragolumab will be considered promising for ctDNA-positive stage II melanoma patients.

Randomization will only happen in the stage 1. In total, 36 patients (18 per arm) will be randomly assigned in a 1:1 ratio to the treatment group (atezolizumab and tiragolumab) or reference group (atezolizumab monotherapy). There is no randomization in stage 2. Stage 2 is single-arm (i.e., the treatment arm only), with a sample size of 25.

According to PI's personal communication with the Natera team, we assume the ctDNA positive rate will be 25%. In stage 1, it is expected that up to 144 patients will be screened in order to randomize 36 patients (18 to each arm). If we continue the study to stage 2 with the treatment arm only, an additional 100 patients will be screened (in order to enroll 25 patients). In total, we expect to accrue 244 patients for ctDNA testing with 61 patients going on to treatment.

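### Section 14.7.1 sets one toxicity criterion but two conflicting monitoring schedules, and reports no stopping probabilities for either

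*Combined protocol and SAP*

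**What the plan says.** Section 14.7.1 monitors treatment-related adverse events of grade 3 or higher, pooled over the combination and the monotherapy arm. The criterion is a posterior probability above 0.80 that the toxicity rate exceeds 20%, the highest rate the plan allows, under a Beta(0.5, 0.5) prior. Monitoring is described as sequential and begins once 12 evaluable patients are available. The action is then given twice:

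- **Text:** "Enrollment will be stopped early whenever there is >80% chance that the event rate is larger than the null".
- **Table:** the trial is recommended to stop "according to the toxicity stopping boundaries listed in the table below". The boundaries are 4 of 12, 7 of 24, 10 of 36, 12 of 48 and 15 of 61, counted in patients determined to be ctDNA positive.

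The section gives no probability of stopping at any toxicity rate.

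Section 14.5 sizes the trial on clearance alone, by Simon's optimal design "with one-sided alpha = 0.05 and power = 0.8": 18 treatment-arm patients, then "with an additional 25 patients being accrued", with success declared as follows: "If 8 or more ctDNA clearances are observed at the study completion". It does not mention the toxicity rule.

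**The concern.** A stopping rule should give one answer for one set of data. Here the text can be met at any patient from the twelfth on, whereas the table can be met only at five sample sizes. The denominators differ (evaluable patients in the text, ctDNA-positive patients in the table), and so does the force (enrolment stops, against a recommendation to stop the trial). A monitoring board applying the section could therefore stop or continue on the same record, depending on which sentence it follows.

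Without stopping probabilities, nobody approving the plan can see how often either version halts a trial with acceptable toxicity, or how much the choice matters. A reader of Section 14.5 also cannot tell that its power figure is calculated as if no safety stop could occur.

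**Working it through.** **Inputs.** Section 14.5: n1 = 18, continue if at least 3 clear; n2 = 25; success if at least 8 of 43 clear; clearance 10% vs 25%; 61 patients treated in all. Section 14.7.1: Beta(0.5, 0.5) prior, reference rate 0.20, cutoff 0.80, first look at 12, and the five table rows.

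**1. The plan's own figures.** Power = Σ over x = 3 to 18 of P(X1 = x) · P(X2 ≥ 8 − x), with X1 ~ Bin(18, p) and X2 ~ Bin(25, p). This gives 0.8003 at p = 0.25 and a type I error of 0.048 at p = 0.10. The stated 0.80 reproduces, and no toxicity term enters it.

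With x toxicities in n patients, the posterior is P(θ > 0.20) under Beta(0.5 + x, 0.5 + n − x):

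| x / n | Posterior at the boundary | Posterior with one toxicity fewer |
|---|---|---|
| 4 / 12 | 0.874 | 0.688 |
| 7 / 24 | 0.868 | 0.740 |
| 10 / 36 | 0.876 | 0.779 |
| 12 / 48 | 0.809 | 0.703 |
| 15 / 61 | 0.817 | 0.725 |

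Every row is the smallest count that meets the criterion, so text and table agree at the tabled sizes.

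**2. Between the rows.** The smallest count with posterior above 0.80 is:

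| n | 12–13 | 14–18 | 19–22 | 23–26 | 27–30 | 31–35 | 36–39 | 40–43 | 44–48 | 49–52 | 53–57 | 58–61 |
|---|---|---|---|---|---|---|---|---|---|---|---|---|
| Stop at | 4 | 5 | 6 | 7 | 8 | 9 | 10 | 11 | 12 | 13 | 14 | 15 |

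Two examples:

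- Suppose 3 of 12, so neither version stops, and then two more toxicities. The posterior is 0.837 at 4 of 13 and 0.922 at 5 of 14, so the text stops by patient 14 at the latest. The table has no look until 24, where it needs 7; with 6 or fewer the trial continues.
- At 6 of 22 the posterior is 0.808 and the text stops. If the next two patients have no toxicity, 6 of 24 gives 0.740 and passes the table.

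The difference is therefore more than delay: a trial can stop under one version and never stop under the other.

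**3. Probability of halting before patient 61.** This is an exact forward recursion on the cumulative toxicity count, removing paths that reach the boundary. Looks are at 12, 24, 36 and 48 for the table, and at every patient from 12 to 60 for the text. The look at 61 is left out of this quantity only because accrual is then complete.

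| True toxicity rate | Table | Text |
|---|---|---|
| 10% | 3.0% | 5.2% |
| 15% | 14.0% | 21.6% |
| 20% | 37.7% | 50.0% |
| 25% | 66.5% | 77.9% |
| 30% | 87.2% | 93.5% |

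With the look at 61 included, the 20% row becomes 40.9% and 50.4%.

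**4. Conditional effect on power.** If every halt counts as not promising and toxicity is independent of clearance, power = 0.8003 × (1 − halting probability):

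- 10%, table: 0.8003 × 0.9695 = 0.78; text: 0.8003 × 0.9475 = 0.76.
- 15%, table: 0.8003 × 0.8596 = 0.69; text: 0.8003 × 0.7842 = 0.63.
- 20%, table: 0.8003 × 0.6227 = 0.50; text: 0.8003 × 0.4995 = 0.40.

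If a halted trial with 8 or more clearances so far may still be called promising, simulation (400,000 runs) gives about 0.53 and 0.43 at 20%.

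**The case against.** **The text may be the principle and the table its implementation.** There is one criterion, prior and cutoff, and the sentence after the quoted one points to the table. This is a natural reading and may be what was meant; if so, the table column applies. But the text is phrased as sequential and without limit on when it can act, and nothing confines it to the tabled looks. The different denominators and force also remain. A board charter is mentioned in Section 12.0 but is not among the documents.

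**A reader might infer that the 0.80 power is wrong.** It is not. Section 14.5 attributes it to Simon's design, which delivers 0.8003, and quoting efficacy power without the safety rule is common practice.

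**A reader might infer that the real power is 0.40 to 0.50.** The documents do not support that either. The 20% rate is the maximum allowed, and a rule of this kind will often stop there by design. No expected rate of treatment-related grade 3 or higher events is stated; the 48% and 44% in Section 1.7 are all-cause events in lung cancer. At 10% the loss is 2 to 4 points. The lower figures also count every halt as failure, although Section 14.7.1 does not say that clearances already seen are discarded.

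**The halting probabilities are idealised.** They assume that each patient's toxicity outcome is known at each look. Treatment can run for 13 cycles of 28 days, and Section 7.0 tracks events for 90 days afterwards, so many outcomes would be incomplete and fewer halts would fall before full enrolment. Allowing for futility stopping has little effect: about 37% and 49% at 20% toxicity and 25% clearance. Both points stand as qualifications.

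**A reader might infer that the row at 61 is idle because accrual is complete.** The table speaks of stopping the trial, and patients may still be on treatment when patient 61 is counted. That row can act.

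**Conclusion.** The conflict of schedules is real. Text and table apply the same criterion at different times, to differently described patients and with different force, and the same data can stop the trial under one and continue it under the other. The gap in the probability of halting before patient 61 is about 2 points at 10% true toxicity, 8 at 15% and 12 at 20%. These figures assume independent patients, a common toxicity rate in both arms, complete toxicity data at each look and every stopping signal acted on. They leave out futility stopping and the separate hold for a treatment-related death.

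The power point is one of disclosure only. The 0.80 is correct for the efficacy design, and any combined figure depends on a toxicity rate the documents do not give. Which cutoff or schedule is clinically right is not judged here.

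**What to change.** 1. Reconcile the text and table of Section 14.7.1 into one rule with one denominator and one stated action. Either print the boundary for every n from 12 to 61, as in the working, which matches the text; or state that the criterion is applied only at the tabled looks. Keep the row at 61 in both cases.
2. Report the stopping probabilities of the chosen rule over a range of true toxicity rates, such as 10, 15, 20 and 30%, and say how patients with incomplete toxicity follow-up are counted at a look.
3. In Section 14.5, say that the 0.80 power is for the Simon efficacy design alone, before any safety stop. If a combined figure is given, show it as a range by assumed toxicity rate and say how a halted trial is classified.

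The cost is a few sentences and one or two short tables. The sample size and the efficacy boundaries do not change. The rule is best settled before the twelfth patient is evaluable, when monitoring starts.

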3.2 Step Two (Randomization and Treatment) Eligibility

3.2.1 Inclusion Criteria

1. Positive ctDNA test.
2. Normal bone marrow and organ function as defined below:
 - a. Absolute neutrophil count $\geq 1,500/\text{mcL}$
 - b. Lymphocyte count $\geq 500/\text{mcL}$
 - c. Platelets $\geq 100,000/\text{mcL}$
 - d. Hemoglobin ≥ 9.0 g/dL (patients may be transfused to meet this criterion)
 - e. Total bilirubin ≤ 1.5 x IULN or direct bilirubin \leq IULN for participants with total bilirubin levels > 1.5 x IULN; patients with known Gilbert disease must have total bilirubin ≤ 3 x IULN
 - f. AST(SGOT)/ALT(SGPT) ≤ 2.5 x IULN
 - g. Alkaline phosphatase ≤ 2.5 x IULN
 - h. Creatinine clearance ≥ 45 mL/min by Cockcroft-Gault
 - i. Serum albumin ≥ 2.5 g/dL
 - j. INR or PT ≤ 1.5 x IULN unless participant is receiving anticoagulant therapy as long as PT or aPTT is within therapeutic range of intended use of anticoagulants
 - k. aPTT ≤ 1.5 x IULN unless participant is receiving anticoagulant therapy as long as PT or aPTT is within therapeutic range of intended use of anticoagulants
3. ECOG performance status ≤ 1 (see Appendix A)

4. The effects of atezolizumab and tiragolumab on the developing human fetus are unknown. For this reason, women of childbearing potential and men must agree to use adequate contraception (hormonal or barrier method of birth control, abstinence) prior to study entry and for the duration of study participation, for 90 days after the final dose of tiragolumab, and for 5 months after the final dose of atezolizumab. Should a woman become pregnant or suspect she is pregnant while participating in this study, she must inform her treating physician immediately. Men treated or enrolled on this protocol must also agree to use adequate contraception prior to the study, for the duration of the study, and 90 days after completion of the study

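### The toxicity stopping table in 14.7.1 counts ctDNA-positive rather than treated patients, and the 30-day safety window in 14.3 contradicts the 90 days used elsewhere.

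*Combined protocol and SAP*

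**What the plan says.** **Stopping rule (14.7.1).** The event is "study treatment (i.e., the combination of atezolizumab and tiragolumab, or atezolizumab monotherapy) related grade 3 or greater adverse events", pooled over both arms. Monitoring "will be implemented once the first 12 evaluable patients are available". Enrollment stops when the posterior probability that the toxicity rate exceeds 20% is above 0.80, under a Beta(0.5, 0.5) prior. The printed boundaries are 4, 7, 10, 12 and 15 patients with toxicity among 12, 24, 36, 48 and 61. The column holding those five counts is headed "In first # patients being determined ctDNA positive". No adverse event window is given.

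**Who is evaluable (5.3).** "All patients who receive any study treatment are evaluable for toxicity", and they are followed "until a 90-day follow up after the conclusion of treatment or death". In the same section, "Patients in Stage 1 who discontinue treatment prior to C3D1 will be replaced".

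**Where 61 comes from (14.5).** The plan expects to test 244 patients, "with 61 patients going on to treatment". Section 14.6 likewise describes its 43 and 18 as treated patients.

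**What stands between a positive test and a first dose (3.2 and 4.0).** A positive ctDNA test is only the first Step Two criterion. Others include "Normal bone marrow and organ function as defined below", performance status and a list of exclusions, and Step Two must be completed within 16 weeks of resection.

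**Safety window.** Section 14.3 ends safety monitoring 30 days after therapy is discontinued. The schedule of activities, 5.3 and 7.0 all run to 90 days after treatment.

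**The concern.** A patient who is never dosed cannot have a treatment-related event. Counting such patients leaves the numerator unchanged and enlarges the denominator, so the observed rate is diluted and the rule becomes slower to stop. A positive test also precedes dosing, so at any look the header's count can run ahead of the number treated. In a multicenter trial with a numeric rule for stopping enrollment, the monitoring board should know who is counted before the data arrive.

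The window raises a related question about what is counted. A related grade 3 or greater event 45 days after the last dose is collected under 7.0 but lies outside the safety endpoint as 14.3 words it. Because 14.7.1 is silent, nobody can say from the text whether that event counts toward a boundary.

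**Working it through.** **Step 1. Reproduce the plan's table.** Inputs from 14.7.1: prior Beta(0.5, 0.5), limit 0.20, cut-off 0.80. With x events in n patients the posterior is Beta(0.5 + x, 0.5 + n − x), and the boundary is the smallest x whose tail above 0.20 exceeds 0.80.

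| n | printed boundary | posterior tail at boundary | tail with one event fewer |
|---|---|---|---|
| 12 | 4 | 0.874 | 0.688 |
| 24 | 7 | 0.868 | 0.740 |
| 36 | 10 | 0.876 | 0.779 |
| 48 | 12 | 0.809 | 0.703 |
| 61 | 15 | 0.817 | 0.725 |

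All five rows reproduce. The arithmetic of the table is right; only the label on its denominator is in question.

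**Step 2. Which denominator do the documents support?**

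- Rule text, 14.7.1: evaluable patients.
- 5.3: evaluable for toxicity means having received any study treatment.
- 14.5: 61 is the number treated (36 randomized in stage 1 plus 25 in stage 2).
- 14.6: ctDNA-positive patients under treatment.
- Table header, 14.7.1: ctDNA-positive patients, treated or not.

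The header is the outlier.

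**Step 3. What would literal use of the header cost?** The documents do not say what share of ctDNA-positive patients goes undosed, so that share, u, is an assumption. If the true rate among treated patients is r, the rate per counted patient is r(1 − u). With r = 0.30 this is 0.30 × 0.95 = 0.285 at u = 5% and 0.30 × 0.90 = 0.27 at u = 10%. The stopping probability is the exact sequential binomial probability of reaching a boundary, with looks only at the five table rows.

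| true rate r | u | stop by 36 | stop by 61 |
|---|---|---|---|
| 30% | 0 | 77.6% | 91.4% |
| 30% | 5% | 71.9% | 87.1% |
| 30% | 10% | 65.5% | 81.5% |
| 25% | 0 | 56.1% | 71.9% |
| 25% | 5% | 50.0% | 64.8% |
| 25% | 10% | 43.8% | 57.1% |

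The absolute levels depend on the look schedule. If the criterion is instead applied after every patient from the 12th to the 61st, with the boundary recomputed at each count, stopping at r = 30% is 94%, 91% and 86% for u = 0, 5% and 10%. The levels rise, but the direction is unchanged.

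**Step 4. The window.** Set side by side, 14.3 says 30 days; the schedule of activities, 5.3 and 7.0 say 90. The documents do not give the share of events on days 31 to 90, so the effect cannot be sized from them. If 5% or 10% of patients with an event had it only in that interval (an assumption), a 30-day count would scale the rate by the same 0.95 or 0.90, so the figures in step 3 are a ceiling. The real effect on the stopping rule would be smaller: treatment runs up to 13 cycles of 28 days (13 × 28 = 364 days) and accrual is planned over 24 months, so many patients will still be on treatment at a look and have no post-treatment days to count.

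**The case against.** The strongest reply is that a sensible reader can resolve the header. Four places point to treated patients, the boundaries are correct, and the dilution figures need both a literal reading of the header and an assumed undosed share. That is fair as to size, and the percentages are illustrative. It does not remove the contradiction, which sits inside the rule itself and costs only a few words to correct.

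A reader might go further on three points, and the documents do not support any of them.

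- *That replaced stage 1 patients drop out of the count, or that no rule applies beyond 61.* Section 5.3 already keeps every treated patient evaluable for toxicity, and 14.7.1 states its criterion for any point at which the posterior exceeds 80%, not only for the five rows. A reminder would be optional.
- *That the window conflict disables the stopping rule.* It does not. Its main effect is on the endpoint in 14.3, for the reason given in step 4.
- *That pooling the arms is an error and the combination needs its own boundary.* The documents give reasons to pool. Section 1.8.3 expects similar toxicity. Sections 1.7 and 1.8.1 report all-cause grade 3 or greater events of 48% versus 44% and similar grade 3 and 4 immune-mediated events in the lung cancer trial. With assumed rates of 30% on the combination and 26% on monotherapy, the pooled rule stops in 70% of trials by the end of stage 1, against 69% for the same criterion in the combination arm alone. A clear gain needs a wider gap between arms than any section supports. A second binding rule also has a price: when both arms sit at the permitted 20%, simulated full-trial stopping rises from 41% to 50% at the plan's own 0.80 cut-off. Section 12.0 already gives the board toxicities by cohort.

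**Conclusion.** Two inconsistencies stand. The table header in 14.7.1 is wrong as written: it names a population that the rule's own text, 5.3 and 14.5 do not use, and literal use would weaken the rule. At a true 30% rate the loss in the chance of stopping is about 6 or 12 percentage points by 36 patients and 4 or 10 by 61, for assumed undosed shares of 5% and 10% and looks at the five rows. The contradiction itself rests on no assumption.

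The 30-day and 90-day windows contradict each other. Related grade 3 or greater events on days 31 to 90 are collected but fall outside the safety endpoint as 14.3 defines it. The consequence for the stopping rule is smaller and cannot be sized from the documents.

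The printed boundaries are correct, and a separate combination-arm boundary is not a required change. Both corrections should be made; neither calls the design into question.

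**What to change.** 1. In 14.7.1, change the column header to *In first # treated (toxicity-evaluable) patients*. The boundaries 4/12, 7/24, 10/36, 12/48 and 15/61 stay as they are. Optionally, add that replaced stage 1 patients remain in the count, as 5.3 already implies.
2. Reconcile the safety window in 14.3 with the schedule of activities, 5.3 and 7.0, and have 14.7.1 refer to the reconciled window. Which window to adopt is for the sponsor to decide.

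The cost is a few words in one header, one reconciled window and one cross-reference. It needs no new data, no extra patients and no recalculated boundary. If the sponsor wishes, a combination-arm toxicity display could be offered to the monitoring board as an advisory item, but nothing above depends on it.
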